Subjects with an Optimizer device who wish to withdraw from the study will have their device deactivated; in this case, the device charger would be retrieved from the subject in order to eliminate the possibility of further use of the device. Device removal is also an option to the subject at this time.

V. STUDY PROCEDURES AND EVALUATIONS

A. Screening Assessments

Potentially eligible subjects will be informed of the relative risks and potential benefits of participating in the study and then asked to review and sign an IRB-approved informed consent document in accordance with 21§50. A copy of the Informed Consent document template is located in Appendix B. It is recognized that each participating institution shall have their own requirements related to the wording of the informed consent document as well as HIPAA privacy laws. For each subject, a medical history, physical examination, demographic information, medication history (≥ 90 days history) and current usage of medications will be obtained.

B. Baseline Testing

Baseline testing should not be initiated until the subject has been treated for heart failure for at least 90 days and heart failure medications have been stable for a minimum of 30 days as explained in section IV.A.

Subjects will be asked to complete a Kansas City Cardiomyopathy Questionnaire (KCCQ), undergo an NYHA assessment, ECG, 24-Hour Holter, echocardiogram, and blood testing for Creatinine, Hgb, Lymphocyte %, Uric Acid, Total Cholesterol and Sodium.

- An ECG performed within 60 days prior to enrollment may be used as the baseline test and protocol eligibility determination.
- An echocardiogram performed within 60 days prior to enrollment can be used if the baseline heart failure medications requirement was met at the time the test was performed.
- A 24-hour Holter test performed within 60 days prior to enrollment may be used as the baseline test and protocol eligibility determination. Other devices that record all heart beats over a period of 24 hours, that provide total counts of isolated ectopics, couplets, and triplets, may be used, as well (i.e., Zio patch).
- Laboratory values collected within 30 days prior to enrollment may be used for baseline testing requirements.

C. Optimizer Smart Implantation

Eligible subjects will undergo implantation of the OPTIMIZER Smart 2-lead System. Subjects will be prepared for device implantation according to procedures used at the implanting institution. The precordial region of the chest (left or right subclavian region) will be prepped and draped using sterile technique.

After access to the subclavian, cephalic or axillary vein, two ventricular leads (as specified in section II.A.4) will be placed transvenously into the right ventricle for sensing ventricular activity and delivering CCM signals. The preferred lead arrangement is for one RV lead to be placed in the anterior septal position and the other in the posterior position approximately half way between the base and apex. The second most preferred lead arrangement would be for both leads to be positioned in the anterior or posterior septal position with a separation of at least ~2 cm.

Leads that are in place in subjects with a prior ICD and/or pacemaker implant will continue to be used for those devices, and may not be connected to the OPTIMIZER Smart IPG. To ensure that the OPTIMIZER Smart System does not interfere with proper functioning of the ICD or pacemaker, these devices shall be interrogated during application of CCM signals according to the device interaction testing procedure outlined in Appendix D. The main mechanism whereby device interaction could occur is the potential that the CCM signal is sensed and counted in addition to the QRS as an extra electrical depolarization; this is called double counting. To ensure that this is not the case, the ICD/pacemaker should be programmed to its non-therapy delivering mode and the OPTIMIZER Smart System should

be activated to deliver CCM signals. The physician then accesses the marker channels of the ICD/pacemaker to check if double counting is present. If so, the physician should modify the ICD/pacemaker parameters (e.g., increase the blanking period) until double counting is no longer evident.

When the subject is stable and suitable for discharge, a separate pre-discharge chest X-ray (radiography or fluoroscopy) shall be done to rule out pneumothorax and to evaluate lead placement. CCM will be activated and observed prior to discharge with the subject on telemetry; device parameters will be adjusted as needed to ensure proper functioning. Subjects will be introduced to the battery charging system and provided a comprehensive overview on the use of this equipment. Subjects will be discharged with CCM therapy on.

D. 2-Week Follow-up Visit

Approximately 2 weeks after the OPTIMIZER Smart System implant, the subject will return for follow up. The OPTIMIZER Smart IPG will be interrogated to confirm proper functioning and parameters shall be adjusted as needed. In addition, the subject's compliance and understanding with battery charging to maintain CCM therapy ON and the cumulative CCM delivery percentage will be assessed.

E. 30-day Safety Assessment

Each subject will be called approximately 30 days after the index Optimizer Smart System implant procedure to inquire about any and all adverse events, ER visits and Hospitalizations that may have occurred. The hospital/clinic/medical record will be searched for completeness of reporting, as well.

F. 6-Month Follow-up Visit

All subjects will return for follow-up 6 months following the Optimizer Smart System implant. The visit includes a medication review, a physical examination, an NYHA classification, a KCCQ and an OPTIMIZER interrogation. The OPTIMIZER interrogation will include an assessment of the subject's compliance with battery charging to maintain CCM therapy ON and the cumulative CCM delivery percentage will be assessed. OPTIMIZER device-related adverse events (ADEs) and OPTIMIZER serious device-related adverse events (SADEs) shall be reported for the duration of the 6-month study

G. Long-term Follow-up

Following the 6 month follow-up visit, all subjects will be seen at approximately 6 month intervals at the investigational site until FDA has made a determination of device safety and efficacy. These follow-up visits shall include an OPTIMIZER device interrogation and reporting of any ADEs, SADEs, and deaths. In addition, a KCCQ is required at the 1-year visit only.

H. Device retrieval in case of subject death

In the event that a study participant dies, every attempt will be made to secure permission from the family to retrieve the OPTIMIZER IPG and charger. In such cases, the device shall be shipped to the sponsor where it shall be inspected and interrogated.

I. Medications/treatments permitted and not permitted before and/or during the trial

Subjects will remain on their initial medication regimens throughout the study, unless clinical circumstances dictate a change. There are no restrictions on the types of medications that may be used during the trial.

J. Procedures for monitoring subject compliance

Clinical monitoring will be performed by/or under the management direction of the Impulse Dynamics Clinical Research Department.

VI. SAFETY DATA REPORTING REQUIREMENTS AND DEFINITIONS

A. Procedures for recording and reporting adverse events and Intercurrent illnesses

The following safety data and assessments will be collected for safety during the study:

1. Adverse Events (AEs) and Adverse Device Events (ADEs)

All AEs occurring within 30 days of implant will be reported, regardless of their attribution to the device or procedure. An AE is defined as any undesirable change from the subject's baseline and usual health status (prior to their enrollment into the study) whether or not it is device or procedure related. An AE includes device failures that adversely affect the subject and/or require an intervention to correct the failure (ADE). AEs will be further classified by the Investigator for the following:

Optimizer procedure-related: The Investigator will decide whether the AE is considered to be not related, possibility related, definitely related to the Optimizer procedure.

Optimizer device-related: The Investigator will decide whether there is a logical connection between the use of the device and the occurrence of the event (meaning the relationship to the device cannot reasonably be ruled out) and classified as not related, possibility related, definitely related to the Optimizer device.

2. Serious Adverse Device Events/Effects (SADEs)

Serious Adverse Device Events/Effects (SADEs): All SADEs will be reported for as long as the subject is active in the study. An Optimizer device- or Optimizer procedure-related AE shall be classified as “serious” if there is an untoward medical occurrence that results in death, is life-threatening, requires inpatient hospitalization, prolongation of existing hospitalization or invasive treatment, results in persistent or significant disability/incapacity or is a congenital anomaly/birth defect.

- The term “disability” in the definition above refers to substantial disruption of the subject’s ability to conduct normal life functions.
- The term "life-threatening" in the definition above refers to an event that places the patient, in the view of the investigator, at immediate risk of death from the event as it occurred; it does not refer to an event that hypothetically might have caused death if it were more severe or left untreated.

Impulse Dynamics will review serious adverse device events and deaths to determine whether an unanticipated adverse device effect may have occurred.

3. Unanticipated Adverse Device Effect (UADE)

In accordance with CFR 21 § 812.3(s), a UADE is any serious adverse effect on health or safety or any life-threatening problem or death caused by, or associated with, a device, if that effect, problem, or death was not previously identified in nature, severity, or degree of incidence in the investigational plan or application; or any other unanticipated serious problem associated with a device that relates to the rights, safety, or welfare of subjects.

4. Mortality

All deaths, regardless of whether it is related to the study device, study procedure, or not, shall be reported.

B. Procedures for reporting UADEs

1. Investigator Reporting Obligations

The Investigator shall report all safety events defined in section VI.A of the current protocol to Impulse Dynamics and to the reviewing IRB (as/if required according to IRB policy). Serious adverse device events (SADEs) must be reported to Impulse Dynamics within 1 business day after the Investigator learns of the event.

According to 812.150(a), the Investigator is required to submit a report of any UADE occurring during the study to Impulse Dynamics and to the reviewing IRB as soon as possible, but in no event later than 10 working days after he/she first learns of the effect.

2. Sponsor Reporting Obligations

In accordance with CFR 21 § 812.46, Impulse Dynamics will immediately conduct an evaluation of any UADE. If Impulse Dynamics determines that a UADE presents an unreasonable risk to subjects, it will terminate all investigations or parts of the investigations presenting that risk as soon as possible. Termination will occur no later than 5 working days after Impulse Dynamics makes this determination and no later than 15 working days after Impulse Dynamics first received notice of the effect.

VII. ASSESSMENT OF EFFECTIVENESS

Change in quality of life, as assessed by the Kansas City Cardiomyopathy Questionnaire.

VIII. ASSESSMENT OF SAFETY

Safety will be assessed by comparing the prevalence of mortality observed in the Continued Access Study (CAS) to the predicted probability of mortality derived from two validated heart failure models [MAGGIC (Meta-Analysis Global Group in Chronic Heart Failure) and SHFM (Seattle Heart Failure Model)]. The objective is to show that the observed prevalence of mortality is not worse than the derived predicted probability of mortality. Two pairwise comparisons (CAS vs. MAGGIC, CAS vs. SHFM) will be performed at 1 year and 3 years. Observed statistical differences will be noted if the two-sided p-value is less than 0.05.

A. Seattle Heart Failure Model (SHFM)

Specific baseline data will be collected in order to predict survival based on the SHFM. Computation of the SHFM score is done with 14 continuous variables and 10 categorical values; a web-based calculator is available to perform the calculation (<http://www.SeattleHeartFailureModel.org>).

B. Meta-Analysis Global Group in Chronic Heart Failure (MAGGIC)

Specific baseline data will be collected in order to predict survival based on the MAGGIC Prognostic Heart Failure Survival Model. The model identifies 13 independent predictors that should be routinely available although provisions have been made by the website (www.heartfailurerisk.org) for one or two variables to be unknown for an individual.

C. Censored and Missing Data

In the SHFM and MAGGIC analyses above, subjects receiving an LVAD or heart transplant, cases of a device explants, and cases of a decision to permanently stop the therapy will be censored at the time of that change of therapy. These will be documented in the CRF, and will not be counted as an event. In any case of interim analysis, for the purpose of the Kaplan-Meier analysis, unless known otherwise, all cases that are under ongoing routine follow-up that have not yet completed the 3 years period shall be assumed to be alive and treated until the date of analysis.

Missing values may be overcome using imputation by the mean value of the cohort, or default values of the model for similar cohorts.

IX. OTHER ASSESSMENTS

Change in heart failure symptoms will be assessed using the NYHA classification assigned by a site clinician according to their standard clinical practice.

X. DIRECT ACCESS TO SOURCE/DATA DOCUMENTS

The investigators and institutions will permit trial-related monitoring, audits, IRB review, and regulatory inspections, providing direct access to source/data and regulatory documents.

XI. QUALITY CONTROL AND QUALITY ASSURANCE

Quality control and quality assurance is the responsibility of the Investigator and designated study staff. Impulse Dynamics clinical representatives will provide training and support to ensure that data quality is optimal (accurate, valid, reliable, complete and reported in a timely manner). Data will be monitored in accordance with Impulse Dynamic's Monitoring procedures. Data used for publication will not identify the subjects; publications will be generated in accordance with Impulse Dynamic's publication policy.

XII. ETHICS

Heart failure is a prevalent health problem throughout the world. Development of therapies to improve heart function to relieve symptoms, reduce hospitalizations and improve survival is a high priority in cardiovascular medicine.

Studies in animals have demonstrated the safety of the OPTIMIZER System with commercially available active fixation leads and the performance of the CCM signal in improving ventricular function. Results of preliminary clinical studies suggest that brief applications of CCM signals do not pose an unreasonable risk to heart failure subjects. The present study represents the next step in the evaluation of this device. The study is justifiable because the potential benefits of using the device outweigh the risks to participating subjects. Prior to the initiation of the study, the Principal Investigator will provide Impulse Dynamics with a copy of the Patient Informed Consent document that has been approved by the IRB at the investigational site. Before enrollment, each subject will be informed of the overall requirements and potential risks and benefits of the study and his/her written consent will be obtained.

Amendments to the protocol will include rationale for the amendment and will be approved by IRBs. Major deviations from the protocol will be recorded and included in the final study report.

XIII. DATA HANDLING AND RECORD KEEPING

The Database Management System used for this study is Clindex. Clindex was developed by Fortress Medical Systems, LLC, has been validated, and is in compliance with the FDA's regulations on electronic signatures and electronic records (21 CFR Part 11). The database resides in a SOC3 certified facility with numerous security controls in place. Data is stored in

encrypted databases that are backed up hourly and the back-ups transferred to an offsite location. Back-up files are also encrypted.

All study data will be entered directly into an electronic data capture system (EDC) by clinical site personnel throughout the course of the study. Access to clinical study information will be based on individuals' roles and responsibilities and will be controlled by login and password provided by the database administrator. The application provides hierarchical user permissions including data entry, data viewing, data querying and data reporting options.

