Class III and IV heart failure patients are at risk for death from their underlying disease, with annual mortality rates ranging from ~20% for Class III patients to as high as ~75% for Class IV patients. With any invasive cardiovascular procedure in heart failure patients there may be added risk of death. Invasive aspects and the associated risks of the OPTIMIZER implant procedure and device system are described below. Additionally, there may be an increased risk of death associated with the application of cardiac contractility modulation therapy. Applying appropriate subject selection criteria, using meticulous techniques and providing attentive post-procedure care will minimize the risks associated with these procedures.

b. Risks of implantation of the OPTIMIZER Smart pulse generator

The risks associated with implantation of the OPTIMIZER Smart pulse generator are similar to those of implanting a permanent pacemaker, which are well characterized and include (but are not limited to) infection, bleeding, pneumothorax, myocardial perforation by the leads and pain at the incision site. Applying appropriate subject selection criteria, using meticulous surgical technique and providing careful post-operative care will minimize the risks associated with these procedures.

c. Arrhythmias and/or palpitations associated with CCM signal application

Arrhythmias may occur as a result of CCM signal application. Arrhythmias may include bradyarrhythmias or tachyarrhythmias as well as ventricular arrhythmias or supraventricular arrhythmias and may be associated with palpitations. These may include sinus bradycardia, complete heart block, junctional rhythm, asystole, sinus tachycardia, atrial fibrillation, atrial flutter, paroxysmal atrial tachycardia, multifocal atrial tachycardia, premature atrial contractions, premature ventricular contractions, nonsustained or sustained ventricular tachycardia, ventricular fibrillation, electromechanical dissociation, or cardiac arrest. Palpitations are commonly reported in patients with heart failure and may or may not be associated with arrhythmias. Safety algorithms intended to minimize the incidence of arrhythmias have been incorporated into the OPTIMIZER Smart System.

d. Myocardial damage

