k. Chest wall sensation, phrenic or device pocket stimulation

CCM signals may cause chest wall sensation or phrenic stimulation. When these have occurred, they have generally been short-lived and have been resolved by reducing CCM signal voltage. Occasionally an invasive procedure may be required to reposition the leads.

l. Neurologic events

In addition to the risks discussed above, patients with heart failure are at risk of transient ischemic attacks (TIA) and stroke.

m. Potential for OPTIMIZER – ICD/Pacemaker interactions

It is possible that the presence of CCM pulses could be sensed by an ICD which could be interpreted as ventricular tachycardia by the ICD. In such a case, an inappropriate ICD shock could be delivered. Similarly, if a pacemaker inappropriately sensed a CCM pulse for a cardiac depolarization, the pacemaker could be inhibited from delivering treatment during a bradycardia (such as a sinus bradycardia). Device interaction testing has indicated that these do not occur when true bipolar ICD leads are used and when both devices are programmed properly. To minimize this risk, all personnel involved with programming the OPTIMIZER Smart device are appropriately trained in proper device programming.

n. Surgical revision of the OPTIMIZER Smart System

There is a potential that any system component could malfunction, become damaged, infected, or, in the case of the leads, become dislodged. System component malfunction or other clinical circumstances (eg, sepsis) may require noninvasive corrective actions or possibly even a surgical revision (repositioning, replacement, or removal) of the malfunctioning component(s).

o. General Medical

Patients with heart failure may experience adverse events related to their underlying disease and such may be encountered during the course of the study. These may include hypotension, dizziness, syncope, worsening renal function, worsening liver failure, anemia, etc.

2. Known Potential Benefits

a. CCM signal application

Based upon available evidence from preclinical laboratory animal studies and preliminary clinical safety studies, application of non-excitatory electrical CCM signals to the heart muscle during the absolute refractory period can increase the strength of the heart's contraction. Subjects receiving CCM signal application may experience improved exercise tolerance, fewer symptoms of heart failure and increased overall quality of life.

b. Medical Management

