APPENDIX D

Device-device Interaction Testing Procedure

Subjects that have a concomitant device (e.g., ICD, pacemaker) will undergo additional testing at the end of the implant procedure to ensure appropriate function of both the Optimizer Smart System and the concomitant device. The following steps summarize the required testing:

1. Program the ICD so that it does not deliver antitachycardia therapy during this test.
2. Program the sensing windows of the Optimizer IPG and ensure that it can be programmed to consistently delivery CCM therapy in the presence of the concomitant device.
3. Activate CCM therapy and evaluate the real-time intracardiac electrograms and marker channels to ensure that CCM therapy does not cause inappropriate oversensing or undersensing during normal sinus rhythm that cannot be resolved through reprogramming or lead repositioning.
4. While CCM therapy is being delivered, ensure that CCM therapy does not cause inappropriate inhibition of bradycardia pacing. In patients that require bradycardia pacing, activate CCM therapy during pacing and evaluate the real-time intracardiac electrograms and marker channels to ensure that CCM therapy does not cause inappropriate inhibition of bradycardia pacing therapy that cannot be resolved through reprogramming or lead repositioning.
5. At the implanting physician's discretion, program the ICD to detect and convert an induced ventricular tachyarrhythmia. Program the Optimizer Smart to deliver continuous CCM therapy. While CCM therapy is being delivered, induce VT/VF and ensure that the implanted ICD can appropriately detect the ventricular tachyarrhythmia. Ensure that CCM therapy does not cause inappropriate undersensing during VT/VF that cannot be resolved through reprogramming or lead repositioning.

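### Section V.C switches the ICD/pacemaker to a non-therapy mode while CCM is activated, with no exception for subjects who need pacing; Appendix D, cited for the same testing, keeps pacing running in them

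*Protocol*

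**What the plan says.** Section V.C (Optimizer Smart Implantation) deals with subjects who already have an ICD and/or pacemaker. It sends sites to the appendix: "these devices shall be interrogated during application of CCM signals according to the device interaction testing procedure outlined in Appendix D". It then explains double counting, in which the CCM signal is counted as an extra depolarization besides the QRS. For that check "the ICD/pacemaker should be programmed to its non-therapy delivering mode" and the Optimizer is set to deliver CCM. If double counting is seen on the marker channels, "the physician should modify the ICD/pacemaker parameters (e.g., increase the blanking period) until double counting is no longer evident".

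Appendix D covers both ICDs and pacemakers, and its aim is "to ensure appropriate function of both the Optimizer Smart System and the concomitant device". Step 1 reads: "Program the ICD so that it does not deliver antitachycardia therapy during this test". Step 3 looks for oversensing or undersensing in normal sinus rhythm. Step 4 looks for inappropriate inhibition of bradycardia pacing and says: "In patients that require bradycardia pacing, activate CCM therapy during pacing". Step 5, at the implanting physician's discretion, tests detection of an induced ventricular tachyarrhythmia.

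Two risk statements bear on this. Section I.E.1.m warns that, if CCM pulses are mistaken for cardiac depolarizations, "the pacemaker could be inhibited from delivering treatment during a bradycardia". Section I.E.1.c lists arrhythmias that may follow CCM signal application: "These may include sinus bradycardia, complete heart block, junctional rhythm, asystole", among others.

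**The concern.** The main text and the appendix it cites give different device states for the same testing. V.C names the pacemaker along with the ICD and asks for no therapy from either. Appendix D switches off only the ICD's antitachycardia function and relies on pacing in subjects who need it.

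A site that works from V.C alone could turn pacing off in a subject who requires it at the moment CCM is first applied. The protocol itself lists bradycardia, heart block and asystole among the possible effects of CCM. If that state were carried into step 4, the check for inhibited pacing could not be done either, because inhibition cannot be seen when the device is not pacing.

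**Working it through.** No arithmetic applies, and the protocol gives no figure to reproduce. The check sets the two texts side by side.

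1. **Same procedure?** Yes. V.C says the interrogation follows Appendix D, and Appendix D includes pacemakers in its scope.

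2. **What is switched off?** In V.C, the therapy of the ICD/pacemaker. In Appendix D step 1, ICD antitachycardia therapy only. None of the five steps in Appendix D stops bradycardia pacing.

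3. **Does therapy include pacing?** In this protocol, yes. Step 4 refers to bradycardia pacing as therapy, and section I.E.1.m describes what a pacemaker delivers in a bradycardia as treatment. On that usage, a pacemaker in a non-therapy mode is not pacing.

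4. **What must be running?** One of the five steps, step 4, needs CCM to be active during pacing in patients who require it. V.C has no matching exception.

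5. **Is there an order that reconciles them?** V.C could be an early check and step 4 a later one. Neither text gives that order, and neither says to resume pacing in between.

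6. **Whom does it touch?**
   - ICD, no pacing need: the V.C phrase can be read as antitachycardia therapy off, which agrees with step 1. No conflict.
   - Pacemaker, or any device in a subject who requires pacing: V.C read literally has pacing off with CCM on, while step 4 has pacing on with CCM on. Conflict.

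7. **How many?** V.C expects some subjects to have a prior ICD and/or pacemaker. Section III.B allows up to 350 subjects at a maximum of 40 sites, but the protocol gives no share with a pacemaker or a pacing need. The number affected cannot be derived.

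**The case against.** The strongest answer is that Appendix D is the operative procedure. It is numbered and describes itself as the required testing, and V.C defers to it before explaining one mechanism in softer language. A site that carries out Appendix D suspends only antitachycardia therapy and reaches step 4 with pacing available. V.C's sentence also concerns double counting alone, which corresponds to steps 1 to 3; it does not claim to test pacing inhibition. Step 4 becomes impossible only if the non-therapy mode is carried through to it, which neither text says.

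Much of this stands. It removes the conflict for an ICD in a subject without a pacing need and makes it likely that trained staff would do the right thing. It does not remove the conflict for pacemakers and subjects who need pacing. V.C names the pacemaker explicitly, gives no exception, and its reference to Appendix D does not say which text prevails.

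A reader might also infer that the suspension has no end, or that subjects could go home with ICD therapy off or with unrecorded settings. The documents do not support that. Step 1 limits the suspension to the test, V.C's parameter changes end when double counting is gone, and Appendix D aims at proper function of both devices. Section I.E.1.m says that personnel who program the Optimizer are trained in device programming. Appendix C lists a Discharge form whose fields are not shown, so it cannot be said that final settings go unrecorded. The lack of an explicit restore-and-confirm line is missing detail about a step already implied, not an error.

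**Conclusion.** The point holds in a narrow form. For a pacemaker, or a subject who requires pacing, V.C and Appendix D conflict, and V.C taken literally withholds pacing while CCM is first applied. This rests on reading therapy to include pacing, as the protocol's own usage does, and on the absence of any stated order or exception.

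The size is small. The exposure occurs at an attended procedure and no estimand, test, sample size or other statistical quantity is touched. It is a minor patient-safety wording correction. It would go too far to say that pacing will in fact be withheld at sites or that the step 4 check cannot be done; both depend on a site following V.C's sentence in isolation from the appendix it cites.

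**What to change.** In section V.C, replace the sentence on the non-therapy mode with wording such as: *For the duration of the test only, ICD antitachycardia therapy should be suspended (Appendix D, step 1); bradycardia pacing should remain on in subjects who require it (step 4).* The instruction to activate CCM and check the marker channels stays. Limiting the pacing clause to subjects who require it keeps V.C in line with step 4 and asks for nothing beyond it.

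Optionally, add a closing line to Appendix D, applying whether or not step 5 is used, to restore and confirm ICD and pacemaker settings. It should name both devices, since pacing is the main concern.

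The cost is a sentence or two of protocol text. The optional line adds a brief non-invasive confirmation in a session where the device is already being programmed.
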